**Figure 4:** (a) Sample original clinical echocardiographic images containing ultrasound contrast agent; (b) Enhanced image of the bubble traces of the same image; and (c) Vectors showing the corresponding velocity distribution and flow direction calculated using the new echo-PIV/PTV procedures. The color map shows the vorticity (angular velocity) distribution (Sampath et al., submitted for publication).

**Figure 5:** (a) A sample instantaneous brain CEUS showing clear bubble traces; and (b) Distribution of RMS values of contrast over time. Bright (red) regions represent regions with rapid motions and dark (blue) regions represent stagnant zones with weak seeding and/or circulation.

### Microbubble Velocity Mapping Technique

As a further advancement to the existing CEUS quantification tools, we developed a novel microbubble velocity mapping technique for quantifying the instantaneous distributions of brain perfusion abnormalities that may serve as an alternative to diffusion-weighted sequence of MRI.

Echocardiographic particle image velocimetry (echo-PIV) has been introduced in recent years to obtain quantitative velocity distributions from CEUS data [25, 26]. However, images acquired from *routine clinical* CEUS are prone to noise as well as spatially and temporally non-uniform distribution of tracers, adversely affecting the quality of data obtained using standard PIV algorithms. Consequently, we have developed an optimized procedure that integrates the image enhancement, PIV, and particle tracking velocimetry (PTV), which tracks individual tracers in time, to process clinical ultrasound images and obtain reliable, time-resolved, two-dimensional velocity distributions from non-uniformly distributed bubbles [27]. So far, to demonstrate the clinical value of the optimized procedures, the new tools have been used for analyzing cardiac contrast images acquired from four patients with left ventricular thrombus (LVT). A sample original contrast echo image is presented in Figure 4a, the enhanced traces are shown in Figure 4b, and the corresponding velocity and vorticity distributions calculated using the new PIV/PTV procedure is presented in Figure 4c. Time series of such velocity maps enable us to follow the formation, decay and fragmentation of the left-ventricular vortex (large swirling structure in Figure 4c) as it migrates towards the LV apex. The flow induced by this vortex is believed to play a key role in apical washing, an important factor in determining susceptibility to LVT formation. Furthermore, the velocity distribution enables direct quantification of the local washing around the LVT, which might be useful for assessing risk of LVT. A sample of a recently acquired brain CEUS is presented in Figure 5a. The bubble traces are clear and can be readily followed in time. In some areas, they move at high speed while in others, they are slow or even stagnant. As a preliminary indication of the advantages offered by mapping the velocity, Figure 5b shows the root mean square (RMS) of the contrast intensity over time. Bright areas indicate high speed flow regions, and dark regions indicate sites with weak or no flow. Our objective is to integrate the new procedures into routine CEUS imaging, providing bedside real time data on the velocity distribution, flow directions, and clearance rates of injured brains.

The goal of the study is to perform contrast enhanced ultrasound (CEUS) for diagnosis and monitoring of brain injury in neonates and infants. The CEUS technique offers several advantages over MRI in that the technique can be performed at bedside, at lower cost, and without the need for sedation, and thus may serve as a valuable alternative to MRI in critically ill neonates and infants. Our preliminary evidence has shown that CEUS can delineate regions of brain injury due to associated altered perfusion. Extensive literature demonstrates the value of monitoring injury associated perfusion response in prognostication and therapy. This study will enroll neonates and infants in the neonatal intensive care unit or pediatric intensive care unit at Children's Hospital of Philadelphia who are already scheduled to receive a standard of care grayscale brain ultrasound scan.

## **1.2 Name and Description of Investigational Product or Intervention**

Sulfur hexafluoride lipid-type A microspheres (Lumason™, Bracco Inc) is FDA-approved ultrasound contrast agent which consist of active ingredients including Sulfur hexafluoride (strength 60.7 mg in 1 mg), Distearoylphosphatidylcholine, DL- (strength 0.19 mg in 1 mg), 1,2-Dipalmitoyl-Sn-Glycero-3-Phospho-(1'-Rac-Glycerol), Sodium Salt (0.19 mg in 1 mg). Inactive ingredients include Polyethylene Glycol 4000 (strength 24.56 mg in 1 mg) and Palmitic Acid (0.04 mg in 1 mg). The sulfur hexafluoride lipid microspheres are composed of SF6 (molecular weight 145.9) gas in the core surrounded by an outer shell monolayer of phospholipids consisting of 1,2-Distearoyl-sn-glycero-3-phosphocholine (DSPC) and 1,2-Dipalmitoyl-sn-glycero-3-phosphoglycerol, sodium salt (DPPG-Na) with palmitic acid as stabilizer. Sulfur hexafluoride lipid-type A microspheres fall under Category B, that is, animal reproduction studies have failed to demonstrate a risk to the fetus and there are no adequate and well-controlled studies in pregnant women. 1,2-Distearoyl-sn-glycero-3-phosphocholine (DSPC), with empirical formula C44H88NO8P, has a molecular weight of 790.6. 1,2-Dipalmitoyl-sn-glycero-3-phospho-rac-glycerol sodium (DPPG-Na), with empirical formula C38H74 NaO10P, has a molecular weight of 745. In pediatric patients, after reconstitution 0.03 mL per kg is administered intravenously. The weight-based dose of 0.03 mL per kg will be repeated twice during a single examination. Following each injection, an intravenous flush of 0.9% Sodium Chloride is injected.

## **1.3 Compliance Statement**

This study will be conducted in full accordance of all applicable Children's Hospital of Philadelphia Research Policies and Procedures and all applicable federal and state laws and regulations including 45 CFR 46. All episodes of noncompliance will be documented. Research will also be conducted in full accordance with Food and Drug Administration (FDA) regulations 21 CFR 50 (Protection of Human Subjects), 21 CFR 56 (Institutional Review Boards) and 21 CFR 312 (Investigational New Drug).

The investigators will perform the study in accordance with this protocol, will obtain consent, and will report unanticipated problems involving risks to subjects or others in accordance with The Children's Hospital of Philadelphia IRB Policies and Procedures and all federal requirements. Collection, recording, and reporting of data will be accurate and will ensure the privacy, health, and welfare of research subjects during and after the study.

## **2 STUDY OBJECTIVES**

The purpose of this study is to evaluate brain perfusion using contrast enhanced ultrasound CEUS in neonates and infants with hypoxic ischemic injury.

### **2.1 Primary Objective (or Aim)**

The primary objective is to identify regions of interest in gray versus white matter to detect the ratio of perfusion changes, in cases of diffuse white matter ischemia.

## **2.2 Secondary Objective (or Aim)**

The secondary objective is to generate a microbubble velocity mapping technique to detect regions of ischemia.

## **3 INVESTIGATIONAL PLAN**

### **3.1 General Schema of Study Design**

Patients scheduled for routine cranial ultrasound as part of clinical care for screening or monitoring of hypoxic ischemic injury will be recruited for the study. Following parental consent, the subject will undergo an investigational CEUS exam, which will be performed separately from any clinically indicated conventional ultrasound. The CEUS exam includes a pre-contrast ultrasound evaluation with FDA-approved technologies (e.g. gray-scale ultrasound, Doppler ultrasound, microvascular imaging). Pre-contrast ultrasound and CEUS duration is of approximately 20 minutes, followed by 60 minutes of monitoring.

#### **3.1.1 Screening Phase**

Potential subjects will be identified by referral from neonatologists of patients during the neonatal or pediatric intensive care unit stay for suspected, at risk of or diagnosed hypoxic ischemic injury and review of orders for cooling blankets, brain imaging and/or EEG exams in neonates.

Before discussing participation in the study, we will confirm eligibility by reviewing the subjects' medical records. Participation will be discussed between the PI and the referring neonatologist. Participation will be discussed with the parents/guardian by the neonatologist and/or radiologist after identification and confirmation of eligibility. Consent of the parents/guardian will be obtained prior to the exam by the PI, co-investigator, or neonatologist co-investigator in a private setting. Questions will be answered by the PI, co-investigator, or referring neonatologist co-investigator.

#### **3.1.2 Study Treatment Phase**

Investigational CEUS scan will be performed separately from clinically indicated conventional US, in the ICU. CEUS will be performed at the time HII is first suspected or diagnosed. A second CEUS may be performed at short-term follow-up (approximately within 1-2 weeks from the first scan) for a total of two CEUS exams of 1 hour and 20-minute duration each.

Injection of Lumason™ contrast agent will be performed via the existing peripheral intravenous line or central line using the FDA-recommended dose of up to 0.03 mg/kg. Contrast-agent injection will be performed twice per CEUS scan to ensure image quality and test reproducibility. In the case of more stable patients without an IV line, a peripheral IV line will be started to conduct the investigational CEUS. Two bolus

injections will be performed to evaluate for dynamic brain perfusion and several 2-minute cine clips as well as static images will be acquired during the exam.

### **3.2 Allocation to Treatment Groups and Blinding**

Not applicable. The CEUS scan will be interpreted by the sponsor-investigator only.

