#### CEUS scan

CEUS duration is of approximately 15 minutes.

CEUS will be performed at the time HII is first suspected or diagnosed. A second CEUS may be performed at short-term follow-up (approximately within 1-2 weeks from the first scan) for a total of two CEUS exams of 1 hour and 20-minute duration each.

Study participation will be complete when the 60-minute monitoring period of the last CEUS to be performed (after the first CEUS in patients who undergo one exam, or after the second CEUS is complete in patients who undergo two exams).

For those neonates/infants not undergoing hypothermia therapy, the first CEUS scan will be performed at the time HII is first suspected or diagnosed and the second CEUS scan will be performed within 24 hours of clinically indicated MRI. It is part of standard of care to obtain a clinically indicated MRI as follow-up of diagnosed or suspected hypoxic ischemic injury.

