#### **4.2.2 CEUS #2**

A second CEUS may be performed at short-term follow-up (approximately within 1-2 weeks from the first scan) for a total of two CEUS exams of 1 hour and 20-minute duration each.

- Record vital signs and baseline assessment prior to injection of contrast
- Perform pre-contrast injection evaluation.
- CEUS scan performed on the same day of MRI exam
- Monitor patient for 60 minutes following the scan for documentation and treatment of potential adverse events

Documentation of any adverse events through 48 hours post-scanning

Study participation will be complete when the 60-minute monitoring period of the last CEUS to be performed (after the first CEUS in patients who undergo one exam, or after the second CEUS is complete in patients who undergo two exams).

The study team will not use sedation or general anesthesia to conduct the research CEUS scans. The lowest mechanical index (MI) possible will be implemented in both CEUS, with a maximum MI value <0.2.

The results of the CEUS imaging will be collected for research purposes only. The results of the CEUS will not be used to direct clinical care decisions, without

confirmation of diagnosis by another medically established diagnostic product or procedure

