#### **4.5.3 Review of diagnostic images from the PACS (iSite Radiology or iSite Enterprise)**

- Review of cranial ultrasound and CEUS images (iSite)
- Review of available MRI images

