### **6 STATISTICAL CONSIDERATIONS**

Up to 100 evaluable patients should be adequate for assessment of clinical feasibility and optimization of protocol. Qualitative analysis will be used as detailed above. Quantitative analysis will be performed by drawing a region of interest in brain segments and compared to control subjects (those with suspected or at risk of HII but turns out to be normal on imaging and clinical evaluation) using non-parametric Wilcoxon testing.

The study will optimize current techniques in the application of contrast ultrasound. For instance in brain imaging, the optimal plane in which to obtain the contrast perfusion kinetics curve is suggested but not established. The region of interest placement for perfusion kinetics quantification is also suggested by few publications, but not established as the standard practice. All this is part of the optimization process that is pivotal to improving the current contrast ultrasound techniques.

Specific analysis plan consists of both qualitative and quantitative assessment in which description of focal perfusion deficit or lesion, for instance, is reported in correlation with clinical information. Perfusion abnormalities will be qualitatively evaluated (absent – 0, mild hypoperfusion – 1, normal – 2, hyperperfusion – 3) and quantitatively (region of interest placed on brain regions for acquisition of wash-in curves using QLab or Qontrast or other similar software). These abnormalities will be correlated to MRI findings as gold standard, non-contrast ultrasound, and clinical information (neurologic exam, hemodynamics, behavioral outcomes) between serial exams. For extremely injured brain cases, nuclear scan (for diagnosis of brain death) instead of MRI may be performed as part of gold standard

The sample size will be based on the available cases, and based on the current number of patients presenting to Children's Hospital of Philadelphia neonatal or pediatric intensive care unit with clinical suspicion for hypoxic ischemic injury. It is estimated that the study will achieve a sample size of up to 50 neonates and infants per year for up to two years.

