### **6.1 Primary Endpoint**

Qualitative analysis of perfusion abnormalities in correlation with clinical MRI results.

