Risks of the administration of the study drug are considered a minor increase above minimal risk, without the prospect of direct benefit. Adverse effects are not dose-dependent, thus risk is not increased by modifying the timing of interventions or increasing the number of contrast-agent injections.

Another risk of the study includes the insertion of a peripheral IV line. This is a no greater than minimal risk procedure, with the main risks of discomfort, bruising, and infection which are generally self-limited. There is a no greater than minimal risk of breach of confidentiality, which is minimized by having all of study personnel undergo HIPAA training.

Interference of CEUS with MRI is not expected since CEUS contrast-agent Lumason clears within minutes after injection. Elimination of Lumason (Sulfur Hexafluoride Lipid-Type A Microspheres) occurs via the lungs in the first minutes following contrast-agent injection (please see Package Insert's section 12.3 Pharmacokinetics for more detail, attached in Application's section 12.02 (3.0)). Additionally, [name], the sponsor-investigator, has also previously performed brain CEUS before MRI in neonatal patients without adverse events.

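### The plan does not mask the CEUS rating in the primary endpoint to MRI, and it describes the readers in three different ways

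*Combined protocol and SAP*

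**What the plan says.** **Endpoint.** Section 6.1 defines the primary endpoint as "Qualitative analysis of perfusion abnormalities in correlation with clinical MRI results". Section 5 makes the CEUS side of this a visual score from 0 (absent flow) to 3 (increased flow). Section 6 adds "These abnormalities will be correlated to MRI findings as gold standard" and allows a nuclear scan in place of MRI for the most severely injured brains.

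**Masking.** Section 3.2 is the only place that addresses blinding: "Not applicable. The CEUS scan will be interpreted by the sponsor-investigator only".

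**Timing.** The first CEUS is done when hypoxic ischemic injury is first suspected or diagnosed. A second is optional. Section 4.2.2 lists it as "CEUS scan performed on the same day of MRI exam". For infants not undergoing hypothermia, Section 4.2 says "the second CEUS scan will be performed within 24 hours of clinically indicated MRI". Section 4.5.3 lists "Review of available MRI images" next to review of the ultrasound and CEUS images and gives no order between them.

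**Readers.** Section 3.2 names the sponsor-investigator alone. Section 5 has the investigator and a second radiologist doing the visual rating, and separately a second interpretation by another reader. The Abstract has the sponsor-investigator performing the analysis and a second radiologist reviewing it.

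**The concern.** When a subjective test is compared with a reference standard, the main safeguard is that the person scoring the test does not know the reference result. A borderline choice between decreased and normal flow can easily be tipped by knowing what the MRI showed. The reported correlation would then partly reflect the MRI itself, and nothing in the study record would show whether it did.

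The reader contradiction adds to this. If one reader scores, there is no check on that reader. If two score independently, the plan needs a rule for disagreement. If the second only reviews the first, the two readings are not independent and inter-reader agreement means little. The plan gives no rule for settling differences, does not say which rating enters the primary analysis, and plans no analysis of inter-reader agreement.

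**Working it through.** **1. The text.** The plan states no figure on this point, so the check is of wording.

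| Question | What the documents give |
|---|---|
| Is the CEUS reader masked to MRI or nuclear scan? | Not stated; Section 3.2 sets blinding aside |
| Is the rating made before MRI is reviewed? | Not stated in Sections 3 to 6 |
| Is the rating locked? | Not stated |
| Who rates? | One reader (3.2); two raters and a second interpretation (5); one analyst plus a reviewer (Abstract) |
| Which rating is primary, and how are differences settled? | Not stated |

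The timing rules in Sections 4.2 and 4.2.2 govern when the scan is acquired. A scan acquired before MRI can still be scored after it, so these rules do not answer the second question.

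**2. Illustration of size.** This is not an estimate of bias in this trial. Inputs:

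- Sensitivity Se = 0.889 and specificity Sp = 0.666, from the 12-neonate study described in Section 1.1. They are borrowed here as the accuracy of a masked read; the protocol does not say that study was masked.
- MRI-positive share p = 0.50 (assumed).
- Fraction f of reads discordant with MRI that move to agree with it (assumed; the documents give no value).
- The rating is reduced to normal (score 2) or not.

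Agreement without influence: A0 = p × Se + (1 − p) × Sp = 0.5 × 0.889 + 0.5 × 0.666 = 0.7775.

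Agreement with influence: A(f) = A0 + f × (1 − A0). At p = 0.5 chance agreement is 0.5, so Cohen's kappa = 2A − 1.

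| f | Agreement | Kappa |
|---|---|---|
| 0 | 0.778 | 0.555 |
| 0.10 | 0.7775 + 0.10 × 0.2225 = 0.800 | 0.599 |
| 0.25 | 0.7775 + 0.25 × 0.2225 = 0.833 | 0.666 |
| 0.50 | 0.7775 + 0.50 × 0.2225 = 0.889 | 0.777 |

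On the correlation scale, phi for the same 2×2 tables goes from 0.57 to 0.61, 0.68 and 0.78.

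**3. Sensitivity to the assumptions**, from f = 0 to f = 0.50:

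- p = 0.30: A0 = 0.3 × 0.889 + 0.7 × 0.666 = 0.733, rising to 0.866.
- p = 0.70: A0 = 0.7 × 0.889 + 0.3 × 0.666 = 0.822, rising to 0.911.
- p = 0.50 with Sp = 0.50: A0 = 0.6945, rising to 0.847.
- p = 0.50 with Sp = 0.90: A0 = 0.8945, rising to 0.947.

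The direction is the same throughout. The amount depends on inputs that the documents do not supply.

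**The case against.** The strongest reply is that the protocol nowhere says the readers will see the MRI first. A reader might infer that they will, from the second CEUS falling on the day of MRI or within 24 hours of it, or from Section 4.5.3 listing the two image reviews together. Neither inference is supported. Same day and within 24 hours do not put MRI first. Section 4.5.3 sits under subject completion and withdrawal and names image sources; it does not describe a joint reading session. Section 9.4.1 points the other way on acquisition: it expects no interference of CEUS with MRI because the agent clears within minutes, and says the sponsor-investigator "has also previously performed brain CEUS before MRI in neonatal patients without adverse events". All of this stands, and it limits the point to what is left unspecified. It does not close the gap, because none of it fixes when the rating is made.

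A second reply is that the study is open-label with no allocation, so blinding does not apply. That is right for treatment groups. Masking a reader to the reference standard is a separate matter.

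A third is that Section 6 frames the work as feasibility and technique optimisation, and that Sections 4.2.2 and 5 bar unconfirmed CEUS results from directing care. That lowers the consequence of a biased correlation. The stated primary endpoint is still correlation with MRI.

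Finally, the illustration rests on assumed inputs, including accuracy figures from a study of 12 neonates. That is accepted; the conclusion does not depend on it.

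**Conclusion.** Two things hold on the text alone. First, no masking of the CEUS rating to MRI or nuclear-scan results is specified, and no time of rating is fixed, although the rating is subjective and its comparison with MRI is the primary endpoint. Second, Section 3.2 contradicts Section 5 on the number of readers, and the Abstract describes a third arrangement, so the primary rating is undefined.

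The possible bias runs toward higher agreement. Its size cannot be derived from the documents. Under the assumptions shown, moving 10% to 50% of discordant reads would add about 2 to 11 percentage points to an agreement of 78%. The documents do not support the stronger statement that readers will know the MRI or that the result will be biased; they leave the question open. The plan should be corrected before ratings are made, since a reader who has seen the MRI cannot be masked afterwards.

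**What to change.** Replace Section 3.2 and bring the Abstract and Section 5 into line with it. Suggested wording:

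> The sponsor-investigator and the second radiologist each rate every CEUS independently, without access to MRI or nuclear-scan results. Disagreements are settled by consensus, still without that access. The consensus rating is the primary rating. The consensus and both individual ratings are dated and locked before MRI or nuclear-scan results are opened. Inter-reader agreement is reported. A scan whose reader had already seen the MRI is flagged and left out in a sensitivity analysis.

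In Section 4.5.3, make MRI review a separate step after the lock. State as a limitation that the sponsor-investigator cannot be masked to clinical course, given the recruitment role in Section 3.1.1 and the safety-monitoring role in Section 9.3.

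**Cost.** A read-order log and some scheduling of reads. No extra reader is needed, because Section 5 already plans two. If coded reading is wanted, identifiers must also be removed from the CEUS images: Section 9.1 codes the data sheets and scoresheets, not the images. Agreement with MRI may look less favourable than it would under unmasked reading.
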